Study recruitment will be conducted online to minimize COVID-19 exposure, with vitamin D distribution primarily delivered by mail to participants' home addresses or by pick-up from community partner locations. Supported by student volunteers and cost-shared staff effort as needed, we will partner with Chicago community organizations to promote and disseminate information about the study to their clients/members during a 2-month promotional campaign. We have established community partners in the Black and Latinx community through our prior work that we will engage as delineated below under Partner Engagement. Promotion and information-sharing strategies will vary by partner, but we expect that, at minimum, partners will send communications to encourage participation and share information about eligibility criteria and how to enroll in the study. The study website will also list pick-up sites for interested participants. Interested participants will be guided to a secure REDCap platform that will provide information about the study and allow

them to virtually enroll and consent to the study, using their email address for enrollment and later survey participation. Enrollment will require completing a 15-minute baseline survey in REDCap that asks about demographics, health and health behaviors (including vitamin D intake and sun exposure), COVID-19 risks. Persons reporting health conditions indicating risk from vitamin D treatment (hypercalcemia, hyperparathyroidism, kidney stones, pregnancy, lactation) or an allergy to vitamin D will be excluded.

Due to lower than anticipated enrollment in both this study and our other NIH Vitamin D study (IRB20-1302), we will merge study populations. Participants graduating from the 6-month NIH study will be contacted via email and offered the opportunity to participate in this study. These “transitional” participants will then be directed to a new consent form to be enrolled in this study. For participants that have graduated from the NIH study prior to the approval of this amendment (amendment #24 for #IRB20-0847), the study team will reach out via email to invite them to participate. These previous graduates will be considered new participants and will complete the same eligibility screening, consent, and baseline survey process as other new participants.

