In addition to these questions, we have added some questions on the baseline and follow-up surveys that evaluate sleep habits as well as additional possible risk factors for COVID-19 outcomes. These risk factors—hypertension, diabetes, and mood—are shown to have possible linkages to vitamin D levels. These factors are receiving increased attention in the context of COVID-19 risk and its relationship to low vitamin D levels. While available evidence suggests there is a link between hypertension/cardiovascular disease, diabetes and metabolism, depression/anxiety, and vitamin D levels, to-date no causal relationship has been established. This is supported by both evidence as recently as this year, as well as earlier studies. Questions about hypertension and diabetes are of our own construction, and questions about depression and anxiety come from validated instruments, the GAD-2 and the PHQ-2. We hope to shed light on the relationship between our outcomes of interest, vitamin D, and these risk factors by asking subjects, both already enrolled and new, about these factors.

Our data management plan will specify procedures to collect, organize, handle, clean, analyze, describe, preserve, destroy, report and share data. We will review self-reported survey data regularly to prevent and monitor missing data. We will record and report all known reasons for study dropout and missing data. For our primary outcome of COVID-19 infection as measured by patient report of clinically confirmed COVID-19 (or viral PCR if available) and COVID-19 seroconversion tests that data collection, hazard models will be used to assess the effect of vitamin D dosing on the outcome. We will first develop hazard ratios for between-group analyses on the primary outcome using log-rank tests, and then Cox proportional hazard models with covariates including vitamin D dose, age, gender, race, ethnicity, sun exposure, exposure of cohabitants,

employment status, and geographic location. Secondary study outcomes of hospitalization, ICU use, mechanical ventilation use and death will be analyzed with longitudinal mixed models with these covariates.

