We estimate statistical power using a simulation model based on conservative estimates of the fraction of Chicagoans already immune but unaware they have had COVID-19 ( $\leq 10\%$ ), monthly incidence of COVID-19 (3%/month for Black and Latinx persons and 1%/month for White persons), size of the true effect of vitamin D on incidence we seek to assess, confidence we wish in that assessment, and length of time participants are followed. Based on this we propose to recruit at least 2,000 participants, yielding 80% power at  $p < 0.05$  to demonstrate a reduction of 20% or more in COVID-19 incidence due to vitamin D within 12 months of randomization.

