Secondary analysis of non-Hispanic White participants living north of 40.0 degrees: We will use a multivariable Cox proportional hazards regression model to estimate an adjusted hazard ratio of the effect of moderate versus low dose vitamin D on the outcome in participants who are non-Hispanic White and whose baseline mailing address latitude is \geq 40.0 degrees. Covariates will mirror those described in the primary analysis, excluding race and ethnicity and baseline geographic location. We prespecify this secondary analysis prior to unblinding because

the NIH trial cited above found stronger evidence of increased time to first COVID-19 infection with vitamin D supplementation among non-Hispanic White participants, and participants in that trial were recruited in the Chicagoland area which has a latitude north of 40.0 degrees. The NIH trial also found stronger evidence of increased time to first COVID-19 infection with vitamin D supplementation among participants who reported an average of ≤ 30 minutes of sun per day.

Additional Analyses

Time-varying analysis: We will use a time-varying, multivariable Cox proportional hazards regression model to estimate an adjusted hazard ratio of the effect of moderate versus low dose vitamin D in each calendar quarter (Q1: January through March, Q2: April through June, Q3: July through September, Q4: October through December) on the outcome in participants whose baseline mailing address latitude is ≥ 40.0 degrees. Covariates will mirror those described in the primary analysis, with the addition of four calendar quarter indicator variables as time-varying covariates. Furthermore, instead of using a single indicator variable for moderate dose vitamin D, we will include four indicator variables for treatment with moderate dose interacted with the time-varying calendar quarter. The reference group for the uninteracted and interacted time-varying calendar quarter indicator variables will be Q1 for low dose vitamin D.

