Missing Data: Assuming missingness at random, we will impute missing values of covariates with multiple imputation by chained equations with 20 imputations. Covariates in the imputation will include the covariates in the primary analysis excluding moderate dose vitamin D. The imputation for the secondary analysis of non-Hispanic White participants living north of 40.0 degrees and the treatment heterogeneity analysis will be performed among the denominator of all participants in the primary analysis.

Statistical Significance and Multiple Testing: Statistical significance will be determined by $p < 0.05$ for the primary analysis and the secondary analysis of non-Hispanic White participants living north of 40.0 degrees with no adjustment for multiple comparisons.

Software: Data analysis will be executed in Stata 18.0.

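### The covariate imputation leaves out treatment arm and names no outcome term, which pulls the secondary subgroup hazard ratio toward the overall one if the effect differs by race/ethnicity

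*SAP*

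**What the plan says.** The SAP's Missing Data paragraph assumes missingness at random and states that "we will impute missing values of covariates with multiple imputation by chained equations with 20 imputations". Its only statement of the predictors is "Covariates in the imputation will include the covariates in the primary analysis excluding moderate dose vitamin D". The primary-analysis covariates are age, sex, race/ethnicity, sun exposure, insomnia, exposure outside work, employment, randomization quarter and latitude group. None of these is an outcome term.

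For the secondary and treatment heterogeneity analyses, the imputation "will be performed among the denominator of all participants in the primary analysis". A participant with unknown race/ethnicity can therefore be imputed into or out of the secondary subgroup.

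The SAP chose that subgroup because an earlier trial "found stronger evidence of increased time to first COVID-19 infection with vitamin D supplementation among non-Hispanic White participants". It tests the subgroup at p<0.05 without adjustment, as it does the primary analysis. The documents give no expected or observed share of missing covariates, and the SAP has no sensitivity analysis limited to participants whose subgroup membership was observed.

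**The concern.** Values imputed without arm and outcome are, given the other covariates, unrelated to the outcome and to the difference in outcome between arms. The imputation model is then incompatible with the Cox models fitted afterwards. The missing-at-random assumption does not cure this, because the problem is present even when data are missing completely at random.

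Some participants imputed as non-Hispanic White belong to the other group and bring that group's treatment effect with them. If infection is also more frequent in that group, they bring more than their share of events. The subgroup HR then moves toward the mixed-population HR. This happens only if the effect differs by race/ethnicity, but that difference is the SAP's own reason for the analysis. The method thus weakens the test in the case it was set up to detect. The same reasoning applies to every heterogeneity subgroup defined by an imputed covariate.

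**Working it through.** The plan states no figure on this point, so there is none to reproduce. The size of the pull was worked out by a formula and by simulation.

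**Inputs from the documents.** 2,000 participants, 1:1 allocation, 12 months of follow-up, 20 imputations. Planning incidence is 3% per month for Black and Latinx persons and 1% for White persons (Protocol, section III).

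**Assumptions.** HR 0.60 in non-Hispanic White participants and 1.00 in others; about 50% non-Hispanic White; 60% at latitude 40.0 or above; 20% random early censoring; a two-sided test. The 3% rate is applied to everyone who is not non-Hispanic White. Only race/ethnicity is missing, completely at random, in a share *m*.

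**Formula.** Let *p* be the non-Hispanic White share, and suppose the covariates predict race/ethnicity weakly. After imputation, a fraction *m*(1−*p*) of the subgroup belongs to the other group. With *p* = 0.5 this is *m*/2. If *r* is the ratio of event rates, the share of subgroup events from misassigned participants is

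*f* = *r*(*m*/2) / [1 − *m*/2 + *r*(*m*/2)],

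and the shift in log HR is about *f* × ln(1.00/0.60) = *f* × 0.511.

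**Result with *r* = 3.** The simulation used 800 replicates, logistic imputation with parameter draws, Rubin's rules, and a mean of 53 subgroup events. The complete-data HR is 0.596.

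| *m* | *f* | *f* × 0.511 | Simulated shift (Monte Carlo SE) | Simulated HR |
|---|---|---|---|---|
| 2% | 0.03/1.02 = 0.029 | 0.015 | 0.017 (0.0015) | 0.606 |
| 5% | 0.075/1.05 = 0.071 | 0.036 | 0.036 (0.002) | 0.618 |
| 10% | 0.15/1.10 = 0.136 | 0.070 | 0.069 (0.003) | 0.638 |
| 20% | 0.30/1.20 = 0.250 | 0.128 | 0.130 (0.005) | 0.678 |

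The standard error of the log HR is 0.29, so the shift is 0.069/0.29 = 0.24 SE at 10% missing and 0.130/0.29 = 0.45 SE at 20%.

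**Other ways to handle the missing values (same scenario).**

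| Method | HR at 10% / 20% | Power at 10% / 20% |
|---|---|---|
| As planned | 0.638 / 0.678 | 34% / 24% |
| Arm and outcome added as main effects | 0.617 / 0.640 | – |
| By arm, with event and Nelson-Aalen hazard | 0.595 / 0.595 | 38% / 36% |
| Observed membership only | 0.596 / 0.594 | – |

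Power with complete data is 41%. At 10% missing, 7 points are lost, of which 38 − 34 = 4 come from the imputation rule. At 20%, 17 are lost, of which 36 − 24 = 12 come from the rule.

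**Variations.**
- Equal incidence (2% per month): 0.603 complete; 0.619 and 0.636 as planned at 10% and 20%.
- No heterogeneity (0.80 in both groups): 0.799 complete; 0.799 and 0.802, so no shift.
- Weaker heterogeneity (0.70 against 0.90, equal incidence): 0.704 complete; 0.709, 0.715 and 0.725 at 5%, 10% and 20%.
- Primary HR in the main scenario: 0.892 complete; 0.891 and 0.890 at 10% and 20%.
- Imputed covariate's own HR in the main scenario: 0.261 complete; 0.306 and 0.354. On the log scale this is shrinkage of about 12% and 23%.
- A second simulation, with 400,000 participants and 1%/3% incidence: 0.622 complete; 0.666 and 0.712.
- A model closer to the SAP's, with thirteen randomization quarters and seven further covariates, run at 2,000 and 1,000 participants: 0.574 to 0.631 at 10% missing, and 0.607 to 0.698 at 20%. Imputation by arm gave 0.576 and 0.615; observed membership only gave 0.572 and 0.612.

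**The case against.** The strongest objection is that little race/ethnicity may be missing. The Protocol (section III) says "Enrollment will require completing a 15-minute baseline survey in REDCap", that survey covers demographics, and latitude comes from the mailing address. At 2% missing the shift is negligible, and at 5% it is about 0.12 SE. This stands: whether the bias matters is unknown until the share missing is reported. For insomnia, the Protocol says "we have added some questions on the baseline and follow-up surveys that evaluate sleep habits". That is a possible source of missing baseline values, but not evidence of them. Insomnia was not simulated, and no document suggests that the effect differs by it.

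The main scenario is also demanding. The documents give no subgroup HR, so 0.60 against 1.00 is assumed. The Chicago incidence figures in Protocol section III give ratios of only 2,845/2,115 = 1.35 and 5,626/2,115 = 2.66. Better predictors reduce the pull too: in one run at 20% missing the HR moved only from 0.601 to 0.629. These points affect the size of the bias, not its direction or cause.

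The wording about what the imputation will include does not strictly rule out an outcome term. The omission is read from the list, and the authors should confirm it. The exclusion of arm is explicit.

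A last objection is that imputing by arm could fail with thirteen quarters and sparse cells. The run with that covariate structure stayed close to the full-data values, so this objection does not stand.

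**Conclusion.** The concern holds. As written, the imputation excludes arm and lists no outcome term, yet it can decide who belongs to a subgroup tested at p<0.05. If the effect differs by race/ethnicity, the subgroup HR is biased toward the mixed-population HR. With HR 0.60 against 1.00, 1% against 3% monthly incidence and half the participants non-Hispanic White, the bias in HR is about 0.01 at 2% missing, 0.04 at 10% and 0.08 at 20%. It is smaller with equal incidence or weaker heterogeneity, and absent without heterogeneity. The HRs, the population shares and the missing shares are all assumptions. The primary treatment HR is not at risk. The change should be made before unblinding, but the point does not undermine the trial's main result.

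**What to change.** Replace the sentence on imputation predictors with one to this effect:

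> *Imputation will be performed separately by masked treatment arm and will include all primary-analysis covariates, the COVID-19 event indicator and the Nelson-Aalen cumulative hazard at each participant's follow-up time.*

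Adding arm and outcome only as main effects is not enough, because the association between arm and outcome must be free to differ by race/ethnicity. Keep the 20 imputations.

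Add a sensitivity analysis that repeats the secondary and heterogeneity analyses among participants whose subgroup membership was observed. Report the share missing for each variable that defines a subgroup.

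The cost is one replaced sentence, one added sentence and a few lines of code. No new data are needed, and masked arm codes preserve the blind.
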